7.6.2. Patient Discontinuation From the Study (End of Study for an Individual Patient)

Patients may discontinue from the study for reasons that include but are not limited to the following:

- Patient withdrawal of consent
- Death
- Lost to follow-up
- Completion of all study assessments

7.7. End of Study

The end of study is defined as the timepoint when the final data point is collected from the last patient in the study. This is when the last patient dies, withdraws consent, completes all study assessments, or is lost to follow-up, whichever comes first. Alternatively, the end of study is when the sponsor decides to terminate the study.

The sponsor has the right to terminate this study at any time. Reasons for terminating the study early include but are not limited to the following:

- The incidence or severity of AEs in this or other studies indicates a potential health hazard to patients
- Overall patient enrollment is unsatisfactory

The sponsor will notify each investigator if a decision is made to terminate the study. Should this be necessary, prematurely discontinued patients must be seen for an EOT Visit and Safety Follow-up Visit as described in Section 7.4 and Section 7.5.1.

The investigators may be informed of additional procedures to be followed to ensure that adequate consideration is given to the protection of the patient's interests. The investigator will be responsible for informing IRBs/IECs of the early termination of the study.

8. STUDY ASSESSMENTS

A table of scheduled study assessments is provided in Appendix 1. Patients will be closely monitored for safety and tolerability throughout the study. All assessments must be performed and documented in the medical record for each patient.

Where applicable, dosing will occur only if the clinical assessment and local laboratory test values (that must be available before any dosing) have been reviewed and found to be acceptable per protocol guidelines.

8.1. Screening Assessments

Screening evaluations will be performed \leq 28 days before the first dose of study drug(s) (refer to Appendix 1 for details). Patients who agree to participate will sign the ICF before undergoing any study-specific screening assessment. The screening period begins on the first day that a screening assessment is conducted. Screening evaluations may be repeated as needed within the screening period. The investigator is to assess patient eligibility according to the latest screening assessment results

Results of standard-of-care tests or examinations performed before informed consent has been obtained and ≤ 28 days before the first dose of study drug(s) may be used for the purposes of screening rather than repeating the standard-of-care tests unless otherwise indicated.

Procedures conducted only during the Screening Visit are described in this section. For the description of assessments that are conducted during screening as well as throughout the study, refer to Safety Assessments (Section 8.2), PK Assessments (Section 8.3), Tumor and Response Evaluations (Section 8.4) sections.

Rescreening under limited conditions may be allowed after consultation with BeiGene (eg, when a patient's laboratory result narrowly misses a laboratory criterion and it is correctable and not due to rapidly deteriorating condition or PD). Rescreening is allowed only once.

8.1.1. Oxygen-Saturation measurement

Patients will undergo an oxygen-saturation measurement (on room air). The measurements will be kept in the patients' records as source documents. The findings will be recorded in the eCRF.

8.2. Safety Assessments

8.2.1. Vital Signs

Vital signs will include measurements of body temperature (°C), pulse rate, and blood pressure (systolic and diastolic). Pulse rate and blood pressure will be measured while the patient is in a spine position after resting for 5 minutes.

8.2.2. Physical Examinations

During the Screening Visit, a complete physical examination will be conducted, including evaluations of 1) the head, eyes, ears, nose, and throat; 2) cardiovascular; 3) dermatological; 4) musculoskeletal; 5) respiratory; 6) gastrointestinal; and 7) neurological systems. Any

abnormality identified during screening will be graded according to NCI-CTCAE version 5.0 and recorded in the eCRF with appropriate disease/condition terms.

At subsequent visits (and as clinically indicated), limited, symptom-directed physical examinations will be performed. New or worsened clinically significant abnormalities are to be recorded as AEs in the eCRF. Refer to Section 9.2 for AE definitions, reporting, and follow-up requirements.

8.2.3. Ophthalmologic Examination

Patients will undergo an eye examination by an ophthalmologist. The findings of each examination will be recorded in the eCRF. Any significant abnormality present at screening should be recorded as medical history if assessed at the screening visit or as an AE if occurring after screening.

8.2.4. Performance Status

Patients will be assessed for performance status. For children ≤ 16 years of age, a Lansky Play-Performance Scale (Lansky et al 1985) will be used, and for those ≥ 16 years of age, the Karnofsky Performance Scale (Mor et al 1984) will be used (Appendix 3).

8.2.5. Laboratory Safety Tests

Local laboratory assessments of clinical chemistry, hematology, coagulation, and urinalysis will be conducted as outlined in Appendix 2 per the timepoints shown in Appendix 1.

If clinical chemistry, hematology, coagulation and urinalysis at screening are not performed ≤ 7 days before study drug administration on Day 1 of Cycle 1, these tests should be repeated and reviewed before study drug administration. After Day 1 of Cycle 1, results are to be reviewed within 72 hours before study drug administration.

The investigator must review the laboratory report, document this review, and record any clinically relevant changes occurring during the study in the AE section of the eCRF. The laboratory reports must be filed with the source documents. Clinically relevant abnormal laboratory findings are those that are not associated with the underlying disease, unless judged by the investigator to be more severe than expected for the patient's condition.

All laboratory tests with values considered clinically abnormal during participation in the study or within 40 days after the last dose of study drug should be repeated until the values return to normal or baseline or are no longer considered clinically significant by the investigator or medical monitor.

- If such values do not return to normal/baseline within a period of time judged reasonable by the investigator, the etiology should be identified where possible and the sponsor notified.
- All protocol-required laboratory assessments as defined in Appendix 2 must be conducted in accordance with the laboratory manual and the Schedule of Assessments (Appendix 1).
- If laboratory values from laboratory assessments not specified in the protocol and performed at the institution's local laboratory result in the need for a change in patient

management or are considered clinically relevant by the investigator (eg, are considered an SAE or an AE or require dose modification), then the results must be recorded in the eCRF.

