9.2.5. Laboratory Test Abnormalities

Abnormal laboratory findings (eg, clinical chemistry, complete blood count, coagulation, or urinalysis) or other abnormal assessments (eg, ECGs, x-rays, or vital signs) that are judged by the investigator as clinically significant will be recorded as AEs or SAEs. This includes clinically significant abnormal laboratory findings or other abnormal assessments that are present at baseline and that significantly worsen during the study. The definition of "clinically significant" is left to the judgment of the investigator. In general, these are the laboratory test abnormalities or other abnormal assessments that:

- are associated with clinical signs or symptoms, or
- require active medical intervention, or
- lead to treatment interruption or discontinuation, or
- require close observation, more frequent follow-up assessments, or further diagnostic investigation.

If a clinically significant laboratory abnormality is a sign of a disease or syndrome (eg, alkaline phosphatase and bilirubin 5 x ULN associated with cholestasis), only the diagnosis (ie, cholestasis) should be recorded on the AE eCRF.

If the laboratory abnormality can be characterized by a precise clinical term per standard definitions, the clinical term should be recorded as the AE. For example, an elevated serum potassium level of 7.0 mEq/L should be recorded as "hyperkalemia."

Observations of the same clinically significant laboratory abnormality from visit to visit should not be repeatedly recorded on the AE eCRF unless the etiology changes. The initial severity of the event should be recorded and the severity or seriousness should be updated any time the event worsens.

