9.3. Definition of a Serious Adverse Event

An SAE is any untoward medical occurrence that, at any dose:

- Results in death
- Is life-threatening

Note: The term "life-threatening" in the definition of "serious" refers to an AE in which the patient was at risk of death at the time of the AE. It does not refer to an AE that hypothetically might have caused death if it was more severe.

• Requires hospitalization or prolongation of existing hospitalization

Note: In general, hospitalization signifies that the patient was admitted (usually involving at least an overnight stay) to the hospital or emergency ward for observation and/or treatment that would not have been appropriate in the physician's office or outpatient setting.

Results in disability/incapacity

Note: The term "disability" means a substantial disruption of a person's ability to conduct normal life functions. This definition is not intended to include experiences of relatively minor medical significance, such as uncomplicated headache, nausea, vomiting, diarrhea, influenza, and accidental trauma (eg, sprained ankle), which may interfere with or prevent everyday life functions but do not constitute a substantial disruption.

- Is a congenital anomaly/birth defect
- Is considered a significant medical AE by the investigator based on medical judgement (eg, may jeopardize the patient or may require medical/surgical intervention to prevent one of the outcomes listed above)

The following are NOT considered to be SAEs:

- Hospitalization for elective treatment of a pre-existing condition that did not worsen from baseline
- Hospitalization for social/convenience considerations
- Scheduled therapy for the target disease of the study, including admissions for transfusion support or convenience

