9.5.4. Progressive Disease

As PD is expected in this study population, the term "disease progression" should not be reported as an AE term. Instead the symptoms, signs, or clinical sequelae that result from PD should be reported as the AE term(s). For instance, in a patient who presents with pleural effusion resulting from PD of metastasis to the lungs, the event term should be reported as "pleural effusion" instead of "disease progression." If a patient experiences fatal multiorgan failure due to PD, the term "multiorgan failure" should be reported as the SAE with death as the outcome, instead of "fatal disease progression" or "death due to disease progression." All nonserious AEs, SAEs, and deaths, regardless of relatedness to PD, should be recorded and reported.

9.5.5. **Deaths**

Death is an outcome and not usually considered an AE. If the only information available is death and the cause of death is unknown, then the death is reported as an AE (eg, "death," "death of unknown cause," or "death unexplained").

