Occasional occurrences of peripheral neuropathy have been reported with dinutuximab beta. Cases of motor or sensory neuropathy lasting > 4 days must be evaluated and non-inflammatory causes such as disease progression, infections, metabolic syndromes, and concomitant medication should be excluded.

Treatment should be permanently discontinued in patients experiencing any objective prolonged weakness attributable to dinutuximab beta administration. For patients with moderate (Grade 2) neuropathy (motor with or without sensory), treatment should be interrupted and may be resumed after neurologic symptoms resolve.

Systemic Infections

Patients are likely to be immunocompromised as a result of prior therapies. As they typically have a central venous catheter in situ, they are at risk of developing systemic infection. Patients should have no evidence of systemic infection and any identified infection should be controlled before starting therapy.

Hematologic Toxicities

Occurrence of hematologic toxicities such as erythropenia, thrombocytopenia, or neutropenia has been reported with dinutuximab beta. Grade 4 hematologic toxicities improving to \leq Grade 2 or baseline values by start of next treatment course do not require dose modification.

Laboratory Abnormalities

Regulatory monitoring of liver function and electrolytes is recommended.

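### Protocol 8.2.5 applies a disease-attribution test to laboratory AEs that 9.2.1 and 9.2.5 do not, so a disease-attributed abnormality can be missing from the AE tables

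*Protocol*

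**What the plan says.** Protocol 8.2.5 tells the investigator to review each laboratory report and to "record any clinically relevant changes occurring during the study in the AE section of the eCRF". It then defines clinical relevance: "Clinically relevant abnormal laboratory findings are those that are not associated with the underlying disease", with the exception "unless judged by the investigator to be more severe than expected for the patient's condition". Whether a change is entered thus depends first on what the investigator thinks caused it.

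Protocol 9.2.1 includes abnormal laboratory findings in the AE definition whether or not they are related to study drug, and makes no exception for the underlying disease. Protocol 9.2.5 requires laboratory abnormalities judged clinically significant to be recorded as AEs or SAEs. The judgment is the investigator's. The guidance opens "In general, these are the laboratory test abnormalities or other abnormal assessments that" and lists four features: accompanying signs or symptoms, a need for treatment, interruption or end of study treatment, or a need for closer follow-up. None concerns cause.

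Two other sections bear on the point less directly. Protocol 9.5.4, on progressive disease, says "All nonserious AEs, SAEs, and deaths, regardless of relatedness to PD, should be recorded and reported". Protocol 9.3 lists among events that are not SAEs "Scheduled therapy for the target disease of the study, including admissions for transfusion support or convenience".

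AE frequency, severity, seriousness and relationship are part of the primary endpoint (Protocol Section 2, SAP 4.1). Protocol 9.6 names the toxicity most exposed to this question: "Occurrence of hematologic toxicities such as erythropenia, thrombocytopenia, or neutropenia has been reported with dinutuximab beta".

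**The concern.** Attribution belongs after recording. Protocol 9.2.3 makes the natural history of the disease one factor to weigh when causality is assigned to an AE. Protocol 10.2.2 and SAP 6.6.2 then count an event with missing causality as treatment-related. Under 8.2.5, attribution to neuroblastoma can stop the event from being entered at all, so neither step applies to it. The event is then absent from the TEAE tables, and its seriousness and relationship are not captured.

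This is a single-arm study in approximately 1 to 3 centers with about 8 patients, so there is no comparator in which the same loss would occur. If sites follow different sections, AE incidence partly reflects which section was read. Any loss runs toward fewer recorded events.

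**Working it through.** There is no plan figure to reproduce. The sample size of 8 comes from a cited PK guideline (Protocol 10.6, SAP Section 5), no hypothesis is tested (SAP 6.3.2), and the documents give neither rates for the individual cytopenias nor any under-recording rate. The check is mainly textual.

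**Step 1: apply both tests to the same abnormality.** Take a laboratory change after first dose that needs treatment and that the investigator would judge clinically significant.

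| Ascribed to | Under 8.2.5 | Under 9.2.1 and 9.2.5 |
|---|---|---|
| Study drug | Entered | Entered |
| Earlier myeloablative therapy or transplant | Entered (not the underlying disease) | Entered |
| Neuroblastoma, worse than expected | Entered (exception applies) | Entered |
| Neuroblastoma, no worse than expected | Outside the definition | Entered |

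The sections disagree in the last row only. Neither refers to the other on this question.

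**Step 2: can the last row occur?** Partial responders are eligible (Protocol 4.1, criterion 4), so residual disease is an available explanation. Entry requires ANC of at least 1.5 and platelets of at least 100 x 10^9/L, and hemoglobin above 80 g/L (criterion 11), so a cytopenia needing treatment would be a real change on study. The exception has no threshold.

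**Step 3: scale at n = 8.** One patient is 1/8 = 12.5 percentage points of a preferred term's incidence. Clopper-Pearson 95% limits are the 0.025 quantile of Beta(x, n - x + 1) and the 0.975 quantile of Beta(x + 1, n - x), with lower limit 0 at x = 0:

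- 4/8 = 50.0% (15.7 to 84.3) becomes 3/8 = 37.5% (8.5 to 75.5).
- 1/8 = 12.5% (0.3 to 52.7) becomes 0/8 = 0% (0 to 36.9).

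**Step 4: chance that a term appears at all.** With true incidence p and unrecorded fraction m, both assumed, the probability of at least one recorded case is 1 - [1 - p(1 - m)]^8.

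| Assumed p | m = 0 | m = 25% | m = 50% |
|---|---|---|---|
| 10% | 57.0% | 46.4% | 33.7% |
| 20% | 83.2% | 72.8% | 57.0% |

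For example, with p = 20% and m = 25%: 1 - 0.85^8 = 72.8%.

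**Step 5: what is untouched.** Protocol 10.2.3 summarizes laboratory parameters by CTCAE grade from the measured values. SAP 6.6.3 adds baseline-to-worst-grade shifts for hemoglobin, platelets, WBC, neutrophils and lymphocytes (and ALT, AST and bilirubin), and lists all laboratory data. None of this needs an AE entry. These outputs do not carry seriousness or relationship.

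**The case against.** The strongest reply is that the gap is narrow and covered elsewhere.

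- **The exception does much of the work.** A reader who stops at the first clause of the definition might infer a blanket exclusion of disease-associated findings. The text does not support that. Given the entry blood counts, the required response before transplant and the exclusion of actively progressive disease (Protocol 4.2), a large fall in platelets could well be judged worse than expected. This stands, and it narrows the gap without closing it.
- **Only the underlying disease is filtered.** One might infer that nearly any cytopenia after transplant can be left out. Cytopenia ascribed to prior therapy or to study drug is not excluded by the wording of 8.2.5. This stands.
- **8.2.5 does not forbid recording.** A site could apply both sections and enter anything that meets either, and nothing would be lost. That is a fair reading, but no text prescribes it, and the sentence in 8.2.5 is worded as a definition.
- **9.2.5 is discretionary too.** True. Aligning the sections removes an inconsistency, not the investigator's judgment.
- **9.3 is not in conflict.** A reader might infer that it contradicts the AE rules, or that it lets an admission for severe cytopenia escape 24-hour reporting. Its lead words limit it to scheduled treatment of the target disease, and it concerns whether an admission is serious, not whether a cytopenia is an AE. The hospitalization and other seriousness criteria in the same section remain. It does not contradict 9.2.1, 9.2.5 or 9.5.4. What remains is ambiguity: transfusion treats a cytopenia rather than the tumor, so the example sits oddly under that heading.
- **9.5.4 is weak support.** It mainly governs how consequences of progression are named and reported. The point rests on 9.2.1 and 9.2.5.
- **The laboratory outputs are a real safeguard.** Hematologic toxicity is not lost from the primary safety assessment, which also draws on laboratory abnormalities (Protocol 10.2). This stands.

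**Conclusion.** The point holds in a limited form. For an abnormality ascribed to neuroblastoma, judged no worse than expected, yet clinically significant, 8.2.5 and 9.2.1/9.2.5 give different answers, and the protocol does not say which prevails. AE-table incidence, seriousness and relationship can therefore be under-counted or vary by site.

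The size is 12.5 points per unrecorded patient for the preferred term concerned, assuming 8 treated patients and no other recorded event of that term in the patient. It would be wrong to read this as a 12.5-point fall in the overall TEAE rate: a patient leaves that count only if no other TEAE is recorded. Protocol 1.2.3 reports hypersensitivity in 63%, capillary leak in 40% and pain as the most prominent reaction, so that is unlikely. The frequency of such omissions cannot be derived from the documents and may be zero; the probabilities in the second table are illustrations under assumed inputs. Graded laboratory summaries and hematology shift tables stand as planned. This is a wording conflict in a primary endpoint that should be corrected, not evidence that toxicity will go unseen.

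**What to change.** In Protocol 8.2.5, replace the sentence defining clinical relevance by disease association with a statement that the laboratory changes to be recorded are as defined in Section 9.2.5. One test then applies, and attribution is recorded only in the causality field under 9.2.3. Align the eCRF completion guidelines.

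As a secondary clarification, state in 9.3 that the exemption for scheduled therapy, including transfusion admissions, does not cover unplanned admissions prompted by a new or worsened cytopenia after first dose; those follow the hospitalization criterion already in that section.

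The cost is protocol and guideline wording, slightly more AE and SAE recording, and a slightly less favorable AE table. No treatment, visit or laboratory test changes.

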8.2.6. Echocardiography/Multigated Acquisition Scan

Patients will undergo ECHO/MUGA scanning. The ECHO/MUGA scan recordings will be kept in the patient's records as source documents. The findings of each examination will be recorded in the eCRF. Any significant abnormality present at screening should be recorded as medical history if assessed at the screening visit or as an AE if occurring after screening.

8.2.7. Electrocardiograms

For safety monitoring purposes, the investigator must review, sign, and date all ECG tracings. Paper or electronic copies of ECG tracings will be kept as part of the patient's permanent study file at the site.

All ECGs are to be obtained before other assessments scheduled at that same time (eg, vital sign measurements, blood draws). The patient should rest in a semirecumbent supine position for ≥ 10 minutes in the absence of environmental distractions that may induce changes in heart rate (eg, television, radio, conversation) before each ECG collection.

At each timepoint (see Appendix 1), 3 consecutive 12-lead ECGs should be performed approximately 2 minutes apart to determine the mean QT interval corrected for heart rate using Fridericia's formula (QTcF) interval.

8.2.8. Adverse Events

AEs will be graded and recorded throughout the study according to NCI-CTCAE version 5.0. Characterization of toxicities will include severity, duration, and time to onset.

All AEs, including SAEs, will be collected as described in Section 9.5.

